*Moderated Blood Flow Restriction after Anterior
Cruciate Ligament Reconstruction*

Identifiers: NCT02911909

Unique Protocol ID: 2004255

Date: 06-14-2019

Date: 06-14-2019
Version Number: 3.1
Principal Investigator: [name], DVM, PhD, OTSC
Application Number: 2004255
Application Title: Moderated blood flow restriction after anterior cruciate ligament reconstruction

Moderated Blood Flow Restriction after Anterior Cruciate Ligament Reconstruction

Principal Investigator: [name], DVM, PhD, OTSC
Department of Orthopaedics
[name]
Email: [contact]
[contact]

Coordinating Site: University of Missouri, Missouri Orthopaedic Institute

Funding: Department of Orthopaedic Surgery, University of Missouri

Hypothesis- Patients in the moderated blood flow (Delfi) restriction group will have significantly increased muscle strength, thigh circumference, HGH and IGF levels, and no significant differences in knee range of motion, Lachman exam, KT2000, IKDC, Tegner, PROMIS surveys, VAS scores, or CK levels compared with standard ACL rehabilitation patients.

Background:

ACL injury is a common and potentially devastating injury. Approximately 80,000 ACL tears occur annually in the United States (1). 50,000 of those will go on to have ACL reconstruction surgery (2). Goals of reconstruction surgery and rehabilitation include: joint stability, restoration of knee function, and return to preinjury activities. The quadriceps is critical to dynamic joint stability, and weakness of this muscle group is related to poor functional outcomes. Because of this, identifying strategies to minimize quadriceps weakness following ACL injury and reconstruction is of great clinical interest (3). Moderated blood flow training, was developed in 1966 by [name] of Japan. This training technique uses specialized pneumatic belts, placed on the upper arms or legs that moderate blood flow to the distal extremity leading to engorgement of blood in the arms and legs. This exercise method has been shown to be safe and effective in producing muscle hypertrophy at lower intensity training (4,5). Typically a training intensity of more than 65% of one repetition maximum (1 RM) is considered the minimum intensity required to achieve muscle hypertrophy and strength gains (6). However, such intensive weight may not be possible or safe in the postoperative patient population. With moderated blood flow training, substantial muscle hypertrophy can occur using a training intensity as low as 20% of 1 RM (6). Moderated blood flow training provides a safe, less intense, but still effective means to promote muscle hypertrophy in the post-operative ACL patient. We hypothesize that patients randomized to standard physical therapy with moderated blood flow training will demonstrate significantly increased muscle strength, muscle mass, HGH, IGF levels, and no significant differences in knee range of motion, Lachman exam, KT2000, VAS scores, and CK levels compared with standard physical therapy without moderated blood flow in post-

operative ACL patients. This in turn could lead to faster, yet safer, return to functional day-to-day activities and sport.

Objectives: To determine if there are significant differences in muscle strength, thigh circumference, knee range of motion, VAS, IKDC, Tegner, PROMIS surveys, HGH, IGF, CK levels, KT2000, and Lachman’s exam in those patients that participate in moderated blood flow postoperative ACL physical therapy vs. standard ACL post-operative physical therapy.

Study Procedures

- a. The study will be a prospective, randomized, controlled trial between two treatment cohorts. A total of 50 patients will be enrolled in the study. Informed consent will be obtained in clinic or by phone (Patient IQ e-consent) prior to any surgical intervention, per the IRB protocol. Enrollees will receive a copy of the consent and HIPAA form. All patients that meet inclusion criteria who consent to participate in the study will then be randomly assigned to either the control group or moderated blood flow therapy group. Randomization will occur by autogenerated permuted 1:1 block randomization using electronic assignment from the orthopaedic research team prior to initiation of post-operative therapy. The control group will undergo standard of care, post-operative ACL reconstruction rehabilitation. The treatment group will also receive standard ACL rehabilitation combined with Delfi moderated blood flow restriction therapy. Patients will follow up at standard of care clinic visits and participate in the same standard of care physical therapy protocol for ACL reconstruction. Baseline measurements of thigh circumference, knee ROM, KT 2000, Lachman exam, and labs for HGH, IGF, and CK will be obtained preoperatively. Patients will also complete preoperative IKDC, Tegner, PROMIS, and VAS pain surveys. Measurements of thigh circumference and knee range of motion will occur at 2 week intervals post operatively. Strength testing will start at 6 weeks post-operatively. These measurements will occur during standard therapy sessions. KT 2000 and Lachman exam will be performed at 4, 6, 8, and 12 months post operatively. A standard functional return to sport evaluation will be performed at the 4, 6, 8, and 12 month postoperative visits. Labs for HGH, IGF, and CK will be drawn at 2, 6, 12, and 24 weeks. VAS pain scores will be recorded before and after each therapy session. The PROMIS, IKDC, and Tegner surveys will be given at 4, 6, 8, 12 month intervals. The study will conclude at 12 month follow up. All post-operative visits will be standard of care. No additional clinic visits will be required for this study. Background patient information will be collected including age, sex, BMI, and co-morbidities.
- b. The control group will be necessary to provide a baseline measure on which moderated blood flow therapy will be compared.
- c. Blinding of the subject will not be possible as the patient will be able to recognize if they have or have not had the moderated blood flow (Delfi) device applied during therapy and application of a sham-device is not practical or considered standard of care. Evaluators performing measurements will be blinded to the patient’s treatment group during assessment of muscle strength, thigh circumference, knee range of motion, Lachman exam, and KT2000. Surgeons will also be blinded to the respective treatment groups. All other outcome measures are objective and quantitative.

Pre-Trial	Investigator discusses study with the patient in person or by phone and provides the patient with a patient Consent Form (in person or electronic)
-----------	--

	Patient provides written consent or electronic consent (Patient IE e-consent) to participate in the study (randomization occurs) IKDC, Tegner, PROMIS, VAS surveys completed. Baseline thigh circumference, ROM, Lachman exam, KT2000 performed Baseline HGH, IGF, CK labs obtained
Day 0	Operative procedure: Documentation of the type of ACL graft used.
Post op Day 1-completion of PT	Patients begin standard physical therapy routine +/- moderated blood flow Thigh circumference, and knee ROM performed every 2 weeks. VAS pain survey recorded before and after each therapy session
Post Op Weeks: 2, 6, 12, 24	Labs for HGH, IGF, and CK levels obtained. Strength testing during routine Physical Therapy visits begins at 6 weeks
4 months post-operatively	Functional return to sport evaluation performed by Physical Therapy IKDC, Tegner, PROMIS, VAS surveys completed. Lachman exam and KT2000 performed.
6 months post-operatively	Functional return to sport evaluation performed by Physical Therapy* IKDC, Tegner, PROMIS, VAS surveys completed. Lachman exam and KT2000 performed.
8 months post-operatively*	Functional return to sport evaluation performed by Physical Therapy IKDC, Tegner, PROMIS, VAS surveys completed. Lachman exam and KT2000 performed.
12 months post-operatively	Functional return to sport evaluation performed by Physical Therapy* IKDC, Tegner, PROMIS, VAS surveys completed. Lachman exam and KT2000 performed Patient will be released from all study activities after the 12 month follow-up visit
* If received as standard of care, data will be collected. If not, data will not be collected	

Withdrawal of Subjects: Subjects will be informed that they have the right to withdraw from the study at any time for any reason, without prejudice to their medical care. The Investigator(s) may elect at any time to withdraw a subject from the study for any reason unrelated to the study if such a decision is in the subject's best medical interest. If a subject discontinues the study prematurely, or is withdrawn by the Investigator(s), as much follow-up data as possible will be obtained. The primary reason for termination or discontinuation will be documented in the report of the final results. Subjects who are withdrawn for any reason from the study after treatment will not be replaced. Subjects who withdraw consent and refuse to complete the follow-up assessment will be considered off-study at that time. Attempts will be made to retrieve any follow-up data, in particular, adverse events at the time of study discontinuation. If the Investigator(s) reports a subject as lost to follow-up, an assistant to the Investigator will ensure that documentation is complete regarding the reason(s) this has occurred and will ensure that every attempt is made by the Investigator(s) to contact the subject or significant other persons associated with the subject to determine subject status. Appropriate documentation will consist of at least two documented attempts at contact via telephone by an assistant of the Investigator (s), followed by an attempt to contact via registered US mail or other courier service requiring recipient signature.

1. Inclusion/Exclusion Criteria

Inclusion Criteria:

-Patients between ages 18-40

-Diagnosed with isolated ACL tear and have been indicated to undergo ACL reconstruction

Exclusion Criteria:

- age <18 years old or >40 years old
- Multiligament knee injury
- Revision ACL reconstruction
- History or peripheral vascular disease
- History of deep vein thrombosis or pulmonary embolism
- Any contraindication to moderated blood flow restriction therapy
- Inability to comply with post-operative ACL reconstruction rehabilitation
- If meniscal repair or a cartilage procedure is performed at the time of surgery that would preclude the patient from being able to follow the standard post-operative ACL rehabilitation.

2. Devices

Delfi's PTS Personalized Tourniquet System (Delfi Medical Innovations Inc., Vancouver, Canada), a form of moderated blood flow training, has been used by the Missouri Orthopaedic Institute Department of Physical Therapy for its proven safety and effectiveness in help to promote muscular strength gains, enhance sports performance, and to assist with rehabilitation from injury or surgery.

Moderated blood flow training causes increased blood pooling in the limbs. During exercise lactic acid is then produced. Due to the moderation of blood flow, the lactic acid is retained longer in the muscles. Hypoxia, acidosis, inorganic phosphate, AMP and other local factors have been shown to turn on transcription, and thus, protein synthesis in muscle cells. This local effect results in stimulation of muscle, tendon and vascular growth (5). Muscle receptors also send stronger signals to the brain which in turn causes large quantities of growth hormone to be released. Under the condition of moderated blood flow therapy, it has been shown that even short-term and low-intensity exercise can induce muscle strength, hypertrophy and increasing muscle mass (7-9).

3. Study Statistics

- a. Primary outcome variable will be muscle strength determined by a trained observer blinded to therapy cohort and time point.
- b. Secondary outcome variables will include: thigh circumference, VAS pain scores, IKDC, Tegner, PROMIS surveys, knee range of motion, KT 2000, Lachman exam, lab levels of HGH, IGF, and CK.
- c. Number of patients per group (n=25) was determined from a pre-study power analysis (t-Test) using previously published data on rehabilitation after ACL reconstruction for a desired power of 0.8 and alpha = 0.05. This analysis resulted in recommended sample size of 20 per group. The N of 25 per group was chosen to allow for subjects lost to follow-up.

4. Risks

- a. Patient confidentiality during the course of this study will be protected in compliance with HIPAA requirements as well as the requirements of the University of Missouri Health-Sciences IRB.

After consent is obtained, all subjects will be assigned a study identification number that requires the use of a key in order to decipher a subject's personal identification information. The key will be kept in the Cerner Power Trials database, which is password protected. The study identification number will be used to label all paper data collection instruments.

All subject information in electronic format will be kept in password-protected storage. All subject information in paper format will be kept in locked cabinets in a secured suite at the Missouri Orthopedic Institute or destroyed.

b. There is potential risk of discomfort from application of the pneumatic tourniquets. This is temporary and occurs during the therapy sessions.

c. Due to the venous pooling from vascular constriction, there is a theoretical risk of increased incidence of blood clots, vascular insufficiency, potential muscle injury, oxidative stress, and possible nerve conduction problems. These theoretical risks have not been demonstrated in previous studies specifically investigating the safety of occlusive therapy (10,11).

5. Benefits

a. There is a potential benefit to the moderated blood flow group of increased muscle mass, strength, and ability to progress in therapy at an accelerated rate compared with control patients. If this benefit is found in the treatment group, moderated blood flow therapy may be able to be used in all ACL reconstruction patients. The hope is that the increased strength and muscle mass will allow patients to progress in therapy at a safe and accelerated rate, and therefore allow patients to get back to their preinjury activities. Otherwise, there are no further direct benefits to the patient for participation in the study.

6. Payment and Remuneration

a. No compensation for participation in the study.

7. Costs

a. Patients that choose to participate in the study will not incur any additional costs related to the study. Patients will receive the standard of care surgical procedure and postoperative rehabilitation protocols. Any additional lab tests and study related measurements will be at no charge to the patient and will be covered by the Department of Orthopaedic Surgery.

8. References

(1)Griffin, Letha Y., et al. "Noncontact anterior cruciate ligament injuries: risk factors and prevention strategies." *Journal of the American Academy of Orthopaedic Surgeons* 8.3 (2000): 141-150.

(2) Iwasa, J., Y. Shima, and L. Engebretsen. "Results of ACL reconstruction." *The Knee Joint*. Springer Paris, 2012. 245-262.

(3) Palmieri-Smith, Riann M., Abbey C. Thomas, and Edward M. Wojtys. "Maximizing quadriceps strength after ACL reconstruction." *Clinics in sports medicine* 27.3 (2008): 405-424.

(4) KAATSU-In Layman's Terms. <http://www.kaatsu-global.com/kaatsu-in-laymans-terms/> Accessed 11/9/15.

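### The hypothesis predicts no significant difference on eight secondary outcomes without a margin or interval rule, so a non-significant test counts as the predicted result although it cannot show similarity

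*Combined protocol and SAP*

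**What the plan says.** The Hypothesis statement at the front of the combined protocol and SAP has two halves. It predicts gains in strength, thigh circumference, HGH and IGF, and it predicts "no significant differences in knee range of motion, Lachman exam, KT2000, IKDC, Tegner, PROMIS surveys, VAS scores, or CK levels" relative to standard rehabilitation. Background restates the second half for a shorter list: "no significant differences in knee range of motion, Lachman exam, KT2000, VAS scores, and CK levels". IKDC, Tegner and PROMIS are missing from that version. The next sentence in Background reads "This in turn could lead to faster, yet safer, return to functional day-to-day activities and sport".

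Study Statistics b makes all eight outcomes secondary; its list is "thigh circumference, VAS pain scores, IKDC, Tegner, PROMIS surveys, knee range of motion, KT 2000, Lachman exam, lab levels of HGH, IGF, and CK". Study Statistics c sizes the trial with a t-test at power 0.8 and alpha 0.05: "This analysis resulted in recommended sample size of 20 per group", and "The N of 25 per group was chosen to allow for subjects lost to follow-up".

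The documents give no equivalence or non-inferiority margin, no interval criterion, no analysis method and no power statement for these eight outcomes. The Objectives paragraph is framed as a search for differences on the same outcomes.

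**The concern.** A prediction of non-significance is met whenever the test fails to reject. Noisy measurement and missing data therefore make it easier to meet, whatever the true difference is.

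This matters because several of the eight outcomes bear on harm. KT2000 and Lachman measure laxity. VAS measures pain, and the Risks section lists discomfort from the tourniquet. CK bears on muscle injury, which the same section lists as a theoretical risk. A non-significant KT2000 or CK comparison would fulfil the hypothesis even if the data were compatible with a harm of half an SD or more. An estimate with its interval would tell the reader whether such a harm has been ruled out or the data are simply uninformative.

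**Working it through.** **Inputs from the documents.** 20 evaluable and 25 enrolled per arm, alpha 0.05, t-test, power 0.8 (Study Statistics c); 1:1 allocation (Study Procedures a).

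**Assumptions.** Two-sided test (sidedness is not stated); effects in SD units, because the documents give no SDs; a 0.5 SD benchmark; one time point per outcome; roughly normal data, so the figures are only approximate for Lachman, Tegner and CK. Baseline correlations r = 0.5 and 0.7 show what adjustment could gain; the plan does not specify adjustment.

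**The plan's own figure.** The 20 per group cannot be reproduced, because no effect size or SD is given. Solved backwards, it corresponds to a detectable difference of about 0.91 SD (exact t, two-sided). The step to 25 matches a 20% loss allowance: 20 / (1 − 0.20) = 25.

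**Step 1: width of the interval.** Half-width of the 95% CI = t(0.975, 2n−2) × √(2/n).
- n = 20: 2.024 × 0.316 = 0.640 SD.
- n = 25: 2.011 × 0.283 = 0.569 SD.

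With a sample SD at its true value, even an estimate of exactly zero would leave 0.5 SD inside the interval on both sides.

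**Step 2: chance that a true 0.5 SD difference is non-significant.** Noncentral t with noncentrality 0.5 / √(2/n), which is 1.581 at n = 20 and 1.768 at n = 25. For baseline adjustment, the SD is multiplied by √(1−r²) and one degree of freedom is lost.

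| | n = 20 | n = 25 |
|---|---|---|
| Unadjusted | 0.662 | 0.590 |
| r = 0.5 | 0.572 | 0.484 |
| r = 0.7 | 0.422 | 0.321 |

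**Step 3: what a non-significant result rules out when the arms truly do not differ.** By symmetry, the chance that the 95% CI excludes a 0.5 SD harm on one specified side equals the power at 0.5 SD: 1 − 0.662 = 0.338 at n = 20 and 1 − 0.590 = 0.410 at n = 25. Of this, 0.025 comes from results that are significant in the favourable direction. Non-significant results make up 0.95 of the total. So the chance that the CI fails to exclude the harm, given non-significance, is 1 − (power − 0.025) / 0.95.
- Unadjusted: 1 − 0.313/0.95 = 0.671 (n = 20); 1 − 0.385/0.95 = 0.595 (n = 25).
- r = 0.5: 1 − 0.403/0.95 = 0.576; 1 − 0.491/0.95 = 0.483.
- r = 0.7: 1 − 0.553/0.95 = 0.418; 1 − 0.654/0.95 = 0.312.

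A simulation of 2,000,000 runs per case agrees with these to within 0.001.

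**The case against.** The strongest reply is that the prediction states what the investigators expect and is not a decision rule. The Objectives paragraph describes ordinary difference testing, the outcomes are labelled secondary, and no equivalence aim is named. This stands. A reader might infer that the trial plans to declare equivalence or safety from null tests, but no sentence in the documents says so.

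The link to "This in turn could lead to faster, yet safer, return to functional day-to-day activities and sport" is also weaker than it first looks. The sentence is conditional and follows predicted gains in strength and muscle mass. Background has just contrasted low-load training with loads that may be unsafe after surgery, so the safety word may refer to lighter loading and not to null KT2000 or CK results.

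A reader might also take this as a sample-size defect. It is not. A non-significant test fails to show similarity at any n; the planned size only determines how often the null would mislead.

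Two stronger numerical readings should be avoided.
- Without adjustment and with no true difference, 99.0–99.8% of non-significant results have a CI reaching 0.5 SD in at least one direction. That counts the direction of benefit too. For a safety question the one-sided figures in Step 3 are the relevant ones.
- It would be too absolute to say that the trial can never show two-sided similarity at 0.5 SD. With no true difference, the 95% CI lies within both margins 0.2–1% of the time unadjusted, but 18–36% of the time at r = 0.7.

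Finally, 0.5 SD is a benchmark chosen here and not a documented clinically important difference. Repeated measurements of range of motion and VAS could give more precision than one time point, by an amount that the documents do not allow one to calculate. In the other direction, some later assessments are collected only if received as standard of care, so n there may fall below 20.

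What survives is that the null prediction is half of the stated hypothesis, and the text supplies no criterion for it other than non-significance.

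**Conclusion.** The point holds as one about wording and reporting of secondary outcomes, and it should be corrected. As written, a non-significant result on any of the eight outcomes agrees with the hypothesis without supporting similarity. At 25 to 20 per arm, a true 0.5 SD difference would be missed 59–66% of the time unadjusted, 48–57% at r = 0.5 and 32–42% at r = 0.7. With no true difference, about 60–67%, 48–58% and 31–42% of non-significant results, respectively, would leave a 0.5 SD harm on one specified side open. Baseline adjustment reduces the problem but does not remove it.

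The sizes rest on the assumed SD units, benchmark, correlations and single time point. The conclusion that non-significance is not evidence of similarity rests on none of them. The primary strength comparison is unaffected.

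**What to change.** Replace the null prediction in the Hypothesis and Background with one statement that uses a single outcome list, and carry it into Study Statistics. Suggested text:

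> For knee ROM, Lachman, KT2000, IKDC, Tegner, PROMIS, VAS and CK, the between-arm difference will be reported with a 95% CI at a time point fixed before group results are examined. A non-significant result will not be read as similarity or as evidence of safety.

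Optionally, where the sponsor wants to claim that an outcome is not worse, prespecify a justified margin and the direction of harm for that outcome, and report the result as inconclusive when the CI does not exclude the margin. For scale, with no true difference and no adjustment, the 95% CI would exclude a 0.5 SD harm 34–41% of the time at 20 to 25 per arm.

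The cost is some rewording and the choice of one time point per outcome. No patients, visits or measurements are added. The downside is that many of these secondary comparisons will be reported as inconclusive.

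### Muscle strength, the primary outcome, is the only listed outcome with no pre-operative value; the planned comparison stays valid, but baseline information that could sharpen it is left unused

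*Combined protocol and SAP*

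**What the plan says.** Study Statistics, item a, names the primary outcome: "Primary outcome variable will be muscle strength determined by a trained observer blinded to therapy cohort and time point". It gives no muscle group, device, unit or time point. Item b lists the secondary outcomes: "Secondary outcome variables will include: thigh circumference, VAS pain scores, IKDC, Tegner, PROMIS surveys, knee range of motion, KT 2000, Lachman exam, lab levels". The three laboratory measures are CK, HGH and IGF, so there are 11 secondary outcomes in all.

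Study Procedures, item a, sets the pre-operative battery: "Baseline measurements of thigh circumference, knee ROM, KT 2000, Lachman exam, and labs for HGH, IGF, and CK will be obtained preoperatively". It adds: "Patients will also complete preoperative IKDC, Tegner, PROMIS, and VAS pain surveys". The baseline row of the schedule table agrees: "Baseline thigh circumference, ROM, Lachman exam, KT2000 performed", with the surveys and labs alongside. Strength is in neither list.

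On strength, item a says "Strength testing will start at 6 weeks post-operatively", and the table says "Strength testing during routine Physical Therapy visits begins at 6 weeks". In the table row that runs from post-operative day 1 to the end of physical therapy, "Patients begin standard physical therapy routine +/- moderated blood flow".

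Study Statistics, item c, derives 20 per group from a t-test at power 0.8 and alpha 0.05, and raises this to 25 for loss to follow-up. It mentions no covariate, change score or adjusted model. Age, sex, BMI and co-morbidities are collected (Study Procedures, item a), and graft type is recorded on the day of surgery (schedule table).

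**The concern.** Strength varies between people for reasons unrelated to rehabilitation, such as sex and body size. In an unadjusted comparison of about 20 patients per arm, all of that variation stays in the error term. A pre-treatment covariate would remove part of it. The one outcome on which the trial is sized has no such value of its own, and the plan does not say that related baseline data will be used instead.

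There is a second, conditional risk. The hypothesis speaks of increased strength. An analyst who wants a starting point would find only the 6-week value, which falls after the randomised therapy period has opened. Measuring change from it would subtract any effect already gained by then. Nothing in the plan calls for this, and nothing rules it out.

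**Working it through.** **Inputs from the plan.** n = 20 evaluable per arm, 25 enrolled, power 0.80, alpha 0.05, t-test (Study Statistics, item c); 1:1 allocation (Study Procedures, item a). **Not given:** effect size, SD, sidedness, or any correlation between baseline data and strength. Two-sided testing is assumed.

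**1. The plan's own figure.** Without an effect size, n = 20 cannot be derived forward, so I solved for the standardised difference d that it implies. Power = P(T > t_crit), where T is noncentral t with df = 2n − 2 = 38 and noncentrality λ = d·√(n/2). With t_crit = 2.024, power 0.80 needs λ = 2.875, so d = 2.875/√10 = 0.909 (0.80 if one-sided). The allowance for loss is consistent with a 20% rate: 20/(1 − 0.20) = 25. With all 25 per arm evaluable, power at d = 0.909 is 0.883.

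**2. Adjusting for values already collected.** If k covariate terms explain a share R² of strength variance, λ = 2.875/√(1 − R²) and df = 38 − k. With k = 3 (thigh circumference, sex, BMI), df = 35 and t_crit = 2.030:

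| R² (assumed) | λ | Power | Detectable d at power 0.80 |
|---|---|---|---|
| 0.10 | 3.030 | 0.84 | 0.86 |
| 0.20 | 3.214 | 0.88 | 0.82 |
| 0.30 | 3.436 | 0.92 | 0.76 |

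A fourth term changes these powers by less than 0.001.

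The table treats the covariates as balanced between arms. Chance imbalance inflates the variance on average by 1 + k/(2n − 2 − k − 1) = 1 + 3/34 = 1.088 (exact for normally distributed covariates). The variance factors become 0.90 × 1.088 = 0.979, 0.80 × 1.088 = 0.871 and 0.70 × 1.088 = 0.762, with power about 0.81, 0.85 and 0.89. If the covariates explained nothing, the factor of 1.088 would give power of about 0.76. Three terms therefore pay for themselves once R² passes roughly 1 − 1/1.088 = 8%.

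**3. A pre-operative strength value as single covariate.** R² = r² and df = 37. For r = 0.3, 0.5 and 0.7, power is 0.835, 0.898 and 0.975. These r values are assumed.

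**4. Week 6 used as the baseline (hypothetical).** Let f be the share of the final effect present at week 6, with equal SDs at the two times. A change score targets (1 − f)·0.909 with variance factor 2(1 − r):

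| f (assumed) | r = 0.5 | r = 0.7 | r = 0.8 |
|---|---|---|---|
| 0.25 | 0.56 | 0.77 | 0.91 |
| 0.50 | 0.29 | 0.44 | 0.60 |

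As a covariate, week 6 would shrink the target to 0.909·(1 − r·f). At f = 0.5 that is 0.68 (r = 0.5) or 0.59 (r = 0.7), with power 0.68 or 0.72.

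**The case against.** Randomisation makes a comparison of follow-up strength valid without any baseline. The Hypothesis, the Background and Study Procedures, item b, all describe increased strength relative to the control group, not relative to a first test. The sample size came from a t-test with no covariate mentioned. All of this stands.

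A reader might therefore infer two things that the documents do not support. The first is that the treatment effect will be biased toward zero. That requires week 6 to serve as a baseline, which no section says. The size of any loss also depends on assumed values: with a quarter of the effect accrued, change-score power is 0.56 at r = 0.5 but 0.91 at r = 0.8. The second is that the trial misses its stated power. What is shown is a gain forgone, not a shortfall.

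It is also fair to say that no figure for R² or r appears in the plan. If strength is expressed as a limb ratio or otherwise normalised, sex and body size will explain less of it, and the plan does not define the measure. A new pre-operative strength test cannot be assumed to be quick or free. No strength equipment is named, testing takes place at routine therapy visits, no pre-operative therapy visit is described, and item a promises no extra clinic visits. The schedule table also places randomisation at consent, ahead of the baseline battery, so an effort-dependent test could follow allocation in a patient who cannot be blinded.

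What survives is that relevant pre-treatment data are already collected and the plan makes no use of them for its primary outcome.

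**Conclusion.** The point holds as one of precision. Strength is the only listed outcome with no pre-operative value, and its first measurement comes after the therapy period has opened. The between-group comparison is still unbiased.

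At d = 0.909 and 20 per arm, adjustment for variables already in hand moves power from 0.80 to about 0.84–0.92 if they explain 10–30% of strength variance, or about 0.81–0.89 after allowing for chance imbalance. Both ranges rest on an assumed R² and two-sided testing. At the low end the benefit is close to nil, which is why the covariate list should be short. Use of week 6 as a baseline is a risk to exclude in writing, not a flaw in a stated analysis.

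**What to change.** 1. In Study Statistics, replace the unadjusted t-test for the primary strength comparison with an analysis of covariance at a named time point. Adjust for treatment, pre-operative thigh circumference, sex and BMI. Add graft type only if it has few levels: it is recorded after randomisation, although surgeons are blinded to group. Fix the list before any outcome data are seen, and say how a missing pre-operative value will be handled.
2. State that the 6-week strength value is an outcome and will not be used as a baseline or covariate.
3. Optionally, add a pre-operative strength test of the uninjured leg as a covariate, only if it fits the existing pre-operative assessment and is done before the patient learns the allocation. Its correlation with later strength is unknown.

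Items 1 and 2 need wording only and no new data. Item 1 costs one degree of freedom per covariate term, a small loss if the covariates turn out uninformative, and possibly some missing pre-operative values. The burden of item 3 cannot be judged from the plan.
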